2.3 Estimands

Table 1. Change in ALSFRS-R from baseline to month 6 (V4)

Objective: To estimate the treatment effect (IFB-088 vs. placebo), on the Change in ALSFRS-R assessed at Month 6.
Estimand: Treatment-Policy Strategy
Treatment: IFB-088 or matching placebo

STATISTICAL ANALYSIS PLAN		
InFlectis BioScience	Sponsor: Protocol Number:	InFlectis BioScience P288ALS
VERSION 1.0 NOV 12, 2024		

ESTIMAND	ANALYSIS
Target population	Analysis set
Patients with bulbar-onset amyotrophic lateral sclerosis	Full Analysis Set (FAS) defined as all randomized subjects who received at least one dose of study treatment (even if discontinued prematurely) with non-missing baseline ALSFRS-R value.
Variable	Outcome measure
Change in ALSFRS-R assessed at Month 6	Mean change
Handling of intercurrent events	Handling of missing data

 • Death related to disease progression • Death not related to disease progression. • Drop-out 
Treatment policy will be applied.
	
 • Estimand #1 (primary estimand): Missing data will be handled depending on the type of the intercurrent event (i.e.). - Missing data due to deaths: 
 a) due to disease progression: the ALSFRS-R score at month 6 will be imputed by the worst value (i.e. 0) b) other reason (sudden death included): 
 - if the ALSFRS-R score is not missing at Month 3, the ALSFRS-R score at month 6 will be imputed by linear extrapolation given baseline and Month 3 ALSFRS-R score available values. Note: in the linear extrapolation at month 6, the timepoint of ALSFRS assessment considered at V3 will be the exact calendar date of V3 assessment. Calendar time of V4 will be considered as 180 days. - if the ALSFRS-R score is missing at Month 3, the ALSFRS-R score at month 6 will be imputed by linear extrapolation based on the predicted value in the linear regression model including terms for intercept and baseline ALSFRS-R score estimated within the treatment group to

STATISTICAL ANALYSIS PLAN		
InFlectis BioScience	Sponsor:	InFlectis BioScience
	Protocol Number:	P288ALS
VERSION 1.0 NOV 12, 2024		

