	
which the patient is randomized. Imputed values will be rounded to the nearest integer. Imputed value higher than 48 will be replaced by 48 and imputed value lower than 0 will be replaced by 0.
 
 - Missing data due to drop-outs or withdrawal will be imputed with the same approach used for handling missing data due to deaths for reasons not related to disease progression. Imputed values will be rounded to the nearest integer. Imputed value higher than 48 will be replaced by 48 and imputed value lower than 0 will be replaced by 0. • Estimand #2: Missing data will be handled depending on the type of the intercurrent event (i.e.). 
 - Missing data due to deaths, whatever the cause: the ALSFRS-R score at month 6 will be imputed by the worst value (i.e. 0). - Missing data due to drop-outs or withdrawal will be imputed with the same approach as for Estimand #1 used for handling missing data due to deaths not related to disease progression. Imputed values will be rounded to the nearest integer. Imputed value higher than 48 will be replaced by 48 and imputed value lower than 0 will be replaced by 0. • Estimand #3: Missing data will be handled depending on the type of the intercurrent event (i.e.). 
 -Missing data due to death whatever the cause: the ALSFRS-R score at month 6
--	--

STATISTICAL ANALYSIS PLAN		
InFlectis BioScience	Sponsor: Protocol Number:	InFlectis BioScience P288ALS
VERSION 1.0 NOV 12, 2024		

	
will be imputed by the worst value (i.e. 0).
 
-Missing data due to drop-outs or withdrawal will be replaced by multiple imputation assuming Missing at random and monotone regression. Note: model for multiple imputation will be done without patient who died before V4.
 
Imputed values will be rounded to the nearest integer.

Population-level summary measure	Analysis approach

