
Difference in LS mean changes between IFB-088 and placebo
 
Hodges-Lehmann estimate of the difference between IFB-088 and placebo
	
An analysis of covariance (ANCOVA) model of change from baseline in ALSFRS-R Score to month 6 will be fitted. Adjusted LS means and 95% confidence interval for each treatment group and the difference in LS means along with 95% confidence interval and p-value will be estimated in this ANCOVA model.
 
Estimand # 1 will be considered primarily.
 
Sensitivity analyses considering Estimands # 2 and # 3.
 
Supportive analysis will be performed on the PPS, considering Estimand # 1
 
A non-parametric analysis on the FAS will be performed considering Estimand #1.
 
The Hodges-Lehmann estimate along with the 95% CI and Wilcoxon p-value will be provided.

Table 2: Change in MITOS stage from baseline to month 6 (V4)

Objective: To estimate the treatment effect (IFB-088 vs. placebo), on the change in MITOS stage from baseline to Month 6 (V4).
Estimand: Treatment-Policy Strategy
Treatment: IFB-088 or matching placebo

STATISTICAL ANALYSIS PLAN		
InFlectis BioScience	Sponsor: Protocol Number:	InFlectis BioScience P288ALS
VERSION 1.0 NOV 12, 2024		

ESTIMAND	ANALYSIS
Target population	Analysis set
Patients with bulbar-onset amyotrophic lateral sclerosis	Full Analysis Set (FAS) defined as all randomized subjects who received at least one dose of study treatment (even if discontinued prematurely) with non-missing baseline value.
Variable	Outcome measure
Binary endpoint. Progression is defined as a MITOS stage higher at month than at baseline	Percentage of patients who did not progress to a higher MITOS stage at 6 months compared to baseline.
Handling of intercurrent events	Handling of missing data

 • All -cause deaths • Drop-out Treatment policy will be applied.	Estimand #1 Missing data at month 6 for whichever reason will be considered as progression.
Population-level summary measure	Analysis approach

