3 SAMPLE SIZE

The minimum required sample size for this study has been estimated at 42 evaluable patients. Since it is an exploratory safety study, it has not been based on a formal sample size calculation. However, with regard to the primary safety endpoint, it is worth noting that 28 patients enrolled in the IFB-088 arm will be sufficient to observe at least one SAE which incidence is greater than or equal to 5% (10% resp.) with a probability of at least 76.2% (94.8% respectively). In addition, 42 patients are also considered sufficient to observe some numerical efficacy signal on some key parameters. Assuming a 15% drop-out rate, 50 patients were to be randomised.

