5.11.1.1 Nominal alpha level of significance

As the trial is a safety trial and an estimation efficacy study and as it is not powered for efficacy endpoints, all tests performed on efficacy assessments were planned to be conducted at a 2-sided nominal alpha level of 0.20. 2- sided 95% confidence intervals will be provided.

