5.11.2.2 Change in ALSFRS-R total score from baseline to Month 6 (V4)

5.11.2.2.1 Primary analysis

The primary analysis of the Change in ALSFRS-R total score from baseline to Month 6 will be conducted on the FAS patients with a non-missing baseline ALSFRS-R total score as described in Table 1.

Missing data will be handled as described in Table 1 for estimand #1.

STATISTICAL ANALYSIS PLAN		
InFlectis BioScience	Sponsor:	InFlectis BioScience
	Protocol Number:	P288ALS
VERSION 1.0 NOV 12, 2024		

The change in ALSFRS-R score from baseline to Month 6 will be analyzed using an analysis of covariance (ANCOVA) model including treatment (IFB-088 vs placebo), and baseline ALSFRS-R score as continuous covariates. LS mean change with SE and 95% CI by treatment group and the difference in the LS means between 088 and placebo along with SE and 95%CI and p-value will be provided for estimand #1.

Residuals normality will be checked. Homogeneity of slopes across treatment groups will be investigated in an ANCOVA model including an additional term for treatment by baseline ALSFRS-R interaction.

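### The single regression fill for patients without a Month 3 score makes the primary ALSFRS-R standard error too small, by an amount that depends on a fill rule the SAP leaves unstated

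*SAP*

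**What the plan says.** SAP 2.3, Table 1 makes Estimand #1 primary for the change in ALSFRS-R to Month 6. It treats a missing Month 6 score in three ways:

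- Death from disease progression: scored 0.
- Other death, Month 3 score available: the patient's own line through baseline and Month 3, projected to day 180.
- Other death, no Month 3 score: "imputed by linear extrapolation based on the predicted value in the linear regression model including terms for intercept and baseline ALSFRS-R score", estimated within the randomised arm, then rounded and limited to 0-48.

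Drop-outs follow the second and third rules: "Missing data due to drop-outs or withdrawal will be imputed with the same approach used for handling missing data due to deaths for reasons" unrelated to progression.

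The completed data go into "an analysis of covariance (ANCOVA) model including treatment (IFB-088 vs placebo), and baseline ALSFRS-R score as continuous covariates" (5.11.2.2.1). Table 1 takes from that model "Adjusted LS means and 95% confidence interval for each treatment group and the difference in LS means along with 95% confidence interval and p-value". On the test level, 5.11.1.1 says "all tests performed on efficacy assessments were planned to be conducted at a 2-sided nominal alpha level of 0.20". No residual draw or between-imputation variance is specified.

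Multiple imputation with Rubin's formula appears only for Estimand #3, a sensitivity analysis that scores every death 0. There Table 1 notes that the "model for multiple imputation will be done without patient who died before V4". It says nothing comparable about the Estimand #1 regression, and does not say whether that regression predicts the Month 3 or the Month 6 score.

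The same fill is reused for Estimand #2 drop-outs, the non-parametric analysis (5.11.2.2.4), subgroups (5.11.2.2.6, 5.11.2.4.1), the Month 3 analysis (5.11.2.3), subscores (5.11.2.4) and SVC (5.11.8.1.3).

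**The concern.** A value predicted from baseline within the arm lies on the arm's fitted line. The ANCOVA adjusts for the same baseline, so the filled patient adds almost no residual yet counts as a full observation. Residual variance is understated and sample size overstated, and both errors shrink the reported standard error.

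Such patients are foreseeable. The SAP allows for 15% drop-out. Protocol 5.3 ends data collection at withdrawal apart from a discontinuation visit, and SAP 5.2.5 counts that visit as V3 only on days 83-99. An earlier visit leaves no Month 3 score.

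Progression deaths complicate the size. Against a baseline of at least 36, each zero inflates the residual variance and can hide the shortfall, depending on whether zeros enter the fill regression. That choice also moves the estimate itself. At stake are the confidence interval and test for the lead efficacy estimate. Own-line extrapolation from Month 3 is not criticised here.

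**Working it through.** **The plan's own figures.** 1 - 0.95^28 = 0.762 and 1 - 0.90^28 = 0.948, matching the stated 76.2% and 94.8%. 42/0.85 = 49.4, rounded up to 50. These reproduce. The documents give no SD, standard error or power for ALSFRS-R, so the rest uses scenarios.

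**Inputs from the documents.** 2:1 allocation of 50 (taken as 33:17); 15% drop-out, not split by cause or timing; two-sided alpha 0.20; 95% intervals; baseline at least 36; decline of about one point per month (Protocol 4.2.2.1).

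**Assumptions.** Share lacking Month 3, share of progression deaths (0-6%), SD of change s (4-6 points), and a gap D of 34 points between a zero and the survivors' mean.

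**Approximation without progression deaths.** Per arm of n with share m filled:

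- True variance of the adjusted mean: s²/[n(1 - m)].
- Reported variance: the residual sum of squares comes only from observed patients, so it is about s²(1 - m)/n.
- Reported/true standard error: 1 - m.

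With ratio r, rejection is 2[1 - Φ(1.2816r)] and coverage is 2Φ(1.96r) - 1. For 2, 4 and 8 of 50 filled, r = 0.96, 0.92 and 0.84; rejection is 0.22, 0.24 and 0.28; coverage is 94.0%, 92.9% and 90.0%.

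**Approximation with a share d of progression deaths**, p = 1 - d - m:

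- Zeros in the regression: still 1 - m.
- Zeros out: r = sqrt{[d(1 - d)D² + ps²] / [d(1 - d)D² + (1 - d)²s²/p]}.

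For s = 5, d = 0.04, m = 0.15: d(1 - d)D² = 0.0384 × 1156 = 44.4; ps² = 0.81 × 25 = 20.25; (1 - d)²s²/p = 0.9216 × 25/0.81 = 28.4. So r = sqrt(64.6/72.8) = 0.94, against 0.85 with zeros in.

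**Null simulation** following Table 1 with a Month 6 fill regression: 20,000 runs per cell, 33 v 17, baseline 36-47, slope -1.0 (SD 0.7) points/month, measurement SD 1.5, missing at random, 15% missing in total *including* progression deaths. Each pair is half / all of the other missing patients lacking Month 3. The filled share falls as deaths rise, so rows should be compared with that column in view.

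| Progression deaths | Filled share | Zeros in fill regression | Reported/true SE | Rejection at 0.20 | 95% coverage |
|---|---|---|---|---|---|
| 0% | 7.5 / 15% | n/a | 0.93 / 0.84 | 0.234 / 0.280 | 93.0 / 89.8% |
| 2% | 6.5 / 13% | out | 0.97 / 0.94 | 0.223 / 0.245 | 94.6 / 92.9% |
| 2% | 6.5 / 13% | in | 0.93 / 0.85 | 0.241 / 0.286 | 93.7 / 91.0% |
| 4% | 5.5 / 11% | out | 0.99 / 0.97 | 0.215 / 0.233 | 95.1 / 94.3% |
| 4% | 5.5 / 11% | in | 0.94 / 0.88 | 0.234 / 0.268 | 94.1 / 92.1% |
| 6% | 4.5 / 9% | out | 0.99 / 0.98 | 0.214 / 0.218 | 95.4 / 94.9% |
| 6% | 4.5 / 9% | in | 0.96 / 0.91 | 0.232 / 0.253 | 94.7 / 93.1% |

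The zeros-in ratios track 1 - m. With no deaths and a quarter lacking Month 3, the results are 0.96, 0.219 and 94.2%. If nobody lacks Month 3, rejection is 0.20-0.21 and coverage 95-96% at every death share. A 50-patient trial has no progression death with probability 0.98^50 = 36%, 0.96^50 = 13% and 0.94^50 = 5%; the first row then applies.

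**Effect on the fill.** One zero left in lowers the filled scores in its arm by 1.31 points (IFB-088) or 2.51 (placebo) on average. As a rough check with the planned evaluable numbers, 34/28 = 1.2 and 34/14 = 2.4.

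**Other analyses.** Wilcoxon on the filled data rejects 0.24 / 0.32 with no deaths and 0.24 / 0.28 at 4%, so progression deaths do not restore its level. The Month 3 analysis with 7.5 / 15% filled rejects 0.235 / 0.284 with no deaths; at 2% deaths it rejects 0.221 / 0.243 (zeros out) or 0.243 / 0.296 (zeros in).

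**The case against.** The strongest reply is that little depends on this. Efficacy is secondary and unpowered, multiplicity is not controlled, and no decision rule uses the p-value. The 15% is a sizing allowance, and having every drop-out leave before Month 3 is an extreme case. Protocol 5.3 asks sites to make every effort to obtain the discontinuation visit, and ALSFRS-R is measured there (4.1.9). At half lacking Month 3, rejection stays within 0.21-0.24 and coverage within 93.0-95.4%. This stands and limits the severity. It does not make the interval valid, and the SAP itself describes the efficacy part as estimation, for which intervals are the main output.

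Second, Estimands #2 and #3 both score every death 0 and differ in how drop-outs are handled, so reporting both gives a visible comparison of single fill with pooled imputation. That is useful but imperfect: Estimand #3 also replaces own-line extrapolation, and neither uses the primary death rule.

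Third, the fill may mean predicting Month 3 and then extrapolating. Month 6 zeros from deaths after V3 would then not enter the fit, so the zeros-in rows and the fill shift belong to the Month 6 reading. This stands, and it is a further ambiguity to settle. The understatement remains: under that reading, with no deaths, the ratio is again close to 1 - m (0.92 with 8% filled).

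No magnitude was computed for subscores, subgroups or SVC; they are named because the rule is the same.

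**Conclusion.** The concern holds. When patients without a Month 3 score occur, the primary ANCOVA reports too small a standard error, and nothing elsewhere in the SAP corrects it. The error is in one direction. Without progression deaths it is about 4% of the standard error for 2 of 50 filled and 16% for 8 of 50. With progression deaths it is about 1-6% in the tabled scenarios if zeros are left out of the fill regression, and about the full filled share if they are included. The rule is also incomplete: two programmers could follow it and obtain different primary estimates.

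These are scenarios, not a forecast. They rest on an assumed SD, drop-out timing and progression-death share, and on missingness at random. Restricting progression deaths to the steepest third of slopes changed little (4% deaths: 0.211 / 0.228 with zeros out, 0.240 / 0.271 with zeros in). Given the exploratory status and the Estimand #3 sensitivity analysis, this is a should-fix.

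**What to change.** In Table 1 (Estimand #1) and 5.11.2.2.1, replace the single prediction for patients without a Month 3 score by multiple imputation:

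- Use 50 imputations: Month 3 from treatment and baseline, then Month 6 from treatment, baseline and Month 3.
- Pool the ANCOVA with Rubin's formula, as the SAP's Estimand #3 analysis already does.
- Keep the zero for progression deaths and the own-line extrapolation.
- State that progression deaths and extrapolated Month 6 values are left out of the imputation model.
- Adapt the Estimand #3 code: it drops every patient who died before V4, whereas here non-progression deaths without Month 3 must be imputed.
- Make the same change wherever the fill feeds an ANCOVA: Estimand #2 drop-outs, Month 3, subscores, subgroups and SVC.

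Labelling the Wilcoxon/Hodges-Lehmann result on filled data as descriptive would also help, but that is a preference.

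If the single fill is kept, state which month the regression predicts, whether zeros enter it, and that the standard error omits imputation uncertainty.

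In simulation at 0 / 2 / 4% progression deaths, the fix gave rejection of 0.209 / 0.215 / 0.203 (half lacking Month 3) and 0.202 / 0.212 / 0.209 (all), coverage of 94.3-95.3% and a standard-error ratio of 1.00-1.01. The cost is SAP wording, adapted code and a larger reported standard error. With no progression deaths it rises from 1.28 to 1.39 (half) or 1.20 to 1.44 (all). At 4% deaths with zeros out, it rises from 2.37 to 2.42 or 2.35 to 2.46.

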3 SAMPLE SIZE

The minimum required sample size for this study has been estimated at 42 evaluable patients. Since it is an exploratory safety study, it has not been based on a formal sample size calculation. However, with regard to the primary safety endpoint, it is worth noting that 28 patients enrolled in the IFB-088 arm will be sufficient to observe at least one SAE which incidence is greater than or equal to 5% (10% resp.) with a probability of at least 76.2% (94.8% respectively). In addition, 42 patients are also considered sufficient to observe some numerical efficacy signal on some key parameters. Assuming a 15% drop-out rate, 50 patients were to be randomised.

4 RANDOMIZATION

All participants were centrally randomised in a 2:1 allocation ratio to receive either IFB-088 + riluzole or placebo + riluzole, respectively. No stratification factor was considered. The randomisation was performed through an interactive web response system (IWRS) integrated into the eCRF. Before the study is initiated, the log in information and directions for the IWRS was provided to each site. Once a set of medical characteristics is entered, the IWRS immediately assigned a patient to one of the 2 arms. After the randomisation visit, the investigator automatically received a confirmation by email with the treatment number allocated to the patient.

This is a double-blinded study. Neither participants, nor investigators, nor trial staff, nor the sponsor study team was aware of treatment assignments prior to the database lock at the conclusion of the study.

5 PLANNED ANALYSES

The Statistical Analysis Plan (SAP) and Table, Figure, Listing (TFL) Shells (and any amendments) must be approved prior to breaking of the blind for the analysis. If post final database lock (DBL) additional statistical analyses or changes to the statistical analysis are required, then those will be documented in a post DBL SAP Addendum.

5.1 Analysis Sets

5.1.1 Screened Set

The Screened Set will include all patients that were screened, regardless of whether they were randomized and/or treated or not.

STATISTICAL ANALYSIS PLAN		
InFlectis BioScience	Sponsor:	InFlectis BioScience
	Protocol Number:	P288ALS
VERSION 1.0 NOV 12, 2024		

5.1.2 Randomized Set

The Randomized Set (RS) will include all patients as randomized.

5.1.3 Full Analysis Set

The Full Analysis Set (FAS) is a subset of the RS including all as-randomized subjects who received at least one dose of the IMPs.

The FAS will be considered as the primary set for all efficacy analyses.

5.1.4 Per-Protocol Analysis Set (PPS)

The Per-Protocol Analysis Set (PPS) will include the patients from the FAS with adequate study medication compliance, defined as intake of at least 80% of the planned total dose and having no major protocol violations which could affect the assessment of efficacy. Before database lock, potential patient exclusions from PPS will be reviewed by the Sponsor and documented in a patient evaluability document.

5.1.5 Safety Set (SS)

The Safety Analysis Set includes all patients who received at least one dose of study treatment, even if discontinued prematurely. Patients who received the wrong treatment will be analyzed as actually treated for safety analyses. This analysis set will be used for all safety analyses.

5.2 Derived Data

This section describes the derivations required for statistical analysis. Unless otherwise stated, variables derived in the source data will not be re-calculated.

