4.2.2 Measurements of secondary and exploratory variables

4.2.2.1 *Efficacy assessment*

Efficacy assessment will be performed at baseline (V0), 3 months (V3) and 6 months (V4). It will consist of:

- ALSFRS-R score,
- ALS-MITOS score,
- King's College score,
- Assessment of respiratory function: SVC and ABG. Sniff test will be optional, performed in sites that have the equipment and resources to perform it.
- Bioelectrical Impedance analysis

The ALSFRS-R, which compared to ALSFRS includes also respiratory function, is the most widely used and validated rating instrument for monitoring the progression of disability in patients with ALS. It consists of a disease-specific questionnaire with 12 questions aimed at assessing functionality [\[30-32\]](#). Functional decline averages about one point per month in untreated patients [\[33\]](#).

The ALS-MITOS score is a more recent staging system composed by 4 key domains included in the ALSFRS-R (walking/self-care, swallowing, communicating and breathing). It is a validated tool for predicting long-term survival of ALS patients [\[34, 35\]](#).

The King's College score is based on the number of neurological regions affected and requirement for gastrostomy or non-invasive ventilation [\[36, 37\]](#). While ALS-MITOS staging has greater

resolution for late disease stage corresponding to functional impairment, King's College score is able to differentiate early to mid-disease better, making the two systems complementary [38].

The monitoring of respiratory function is achieved by the measurement of SVC, assessed by spirometry: the patient is asked to take a breath as deep as possible, make a tight seal around the device mouthpiece, and then exhale. In SVC assessment, exhalation is performed slowly. SVC is simple, easy to perform and convenient for serial measurements over a long time to evaluate disease progression [39]. Recently, SVC has been chosen more and more frequently over forced vital capacity (FVC) test in ALS clinical trials as it is easier to perform for the patient while providing equivalent information [40]. However, it can be difficult for bulbar-onset ALS patients who experience facial weakness. The sniff test is a simple, portable, inexpensive test that expects patients to inhale through their noses with one nostril occluded and a probe connected to a pressure transducer. This test is easy to perform also for patients with facial weaknesses [39].

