17.1.2 ALS-MITOS

ALS Milano-Torino Staging (ALS-MITOS)

Date:.....Name patient:.....

Date of Birth:.....

Patient's number.....

ALSFRS domain	Item	Score	Functional score*
Movement (walking/self-care)†	8	4 Normal	0
	Walking	3 Early ambulation difficulties	
		2 Walks with assistance	
		1 Non-ambulatory functional movement only	1
	OR	0 No purposeful leg movement	
	6	4 Normal function	0
Dressing and hygiene	3	3 Independent and complete self-care with effort or decreased efficiency	
		2 Intermittent assistance or substitute methods	
		1 Needs attendant for self-care	1
		0 Total dependence	
Swallowing	3	4 Normal eating habits	0
	Swallowing	3 Early eating problems; occasional choking	
		2 Dietary consistency changes	
		1 Needs supplemental tube feeding	1
		0 NPO (exclusively parenteral or enteral feeding)	
Communicating†	1	4 Normal speech processes	0
	Speech	3 Detectable speech with disturbances	
		2 Intelligible with repeating	
		1 Speech combined with non-vocal communication	1
	AND	0 Loss of useful speech	

	4	4 Normal	0
	Handwriting	3 Slow or sloppy; all words are legible	
		2 Not all words are legible	
		1 Able to grip pen but unable to write	1
		0 Unable to grip pen	
Breathing†	10	4 None	0
	Dyspnea	3 Occurs when walking	
		2 Occurs with one or more of: eating, bathing, dressing	
		1 Occurs at rest, difficulty breathing when either sitting or lying	1
	OR	0 Significant difficulty, considering using mechanical respiratory support	
	12	4 None	0
	Respiratory insufficiency	3 Intermittent use of NIPPV	
		2 Continuous use of NIPPV during the night	1
		1 Continuous use of NIPPV during the night and day	
		0 Invasive mechanical ventilation by intubation or tracheostomy	
ALS-MITOS	Stage	Functional domains lost	
	0	None	
	1	1 domain	
	2	2 domains	
	3	3 domains	
	4	4 domains	
	5	Death	

*Staging determined by the sum of functional score of 1 for each domain.

†Where two items were used, scoring was based on either or both item scores as indicated.

ALFSRS, Amyotrophic Lateral Sclerosis Functional Rating Scale; ALS-MITOS, Amyotrophic Lateral Sclerosis Milano-Torino Staging; NIPPV, nasal intermittent positive pressure ventilation; NPO, nothing to mouth.

Chiò A, et al. *J Neurol Neurosurg Psychiatry* 2013;0:1–7. doi:10.1136/jnnp-2013-306589

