5.2.21 Efficacy endpoints

- ALSFRS-R subscore:

Three subscores will be considered as follows:

- Bulbar subscore: sum of items 1-3
- Motor subcore: sum of items 4-9
- Respiratory subcore: sum of items 10-12

Subscore will be considered as missing if an item is missing.

Note: for motor subscore, item 5 will be considered at missing if item 5a and 5b are missing.

- Worsening (i.e. progression to a higher stage compared to baseline defined by ALS-MITOS score):

Non progression at 6 months (V4) and 3 (V3) months will be derived as follows:

- 0 if ALS-MITOS score is higher at 6 months (or 3 months) compared to ALS-MITOS score at baseline
- 1 if ALS-MITOS score is lower or equal at 6 months (or 3 months) compared to ALS-MITOS score at baseline
- Change in King's College score

Non progression at 6 months and 3 months will be derived as follows:

- 0 if King's College score is higher at 6 months (or 3 months) compared to baseline
- 1 if King's College score is lower or equal at 6 months (or 3 months) compared to baseline
- SVC: percentage of the predicted value for age and sex (%)

Percentage of the predicted value will be calculated according to the formula of predicted FVC in 'Multi-ethnic reference values for spirometry for the 3–95-yr age range: the global lung function 2012 equations' article of Quanjer.

STATISTICAL ANALYSIS PLAN		
InFlectis BioScience	Sponsor: Protocol Number:	InFlectis BioScience P288ALS
VERSION 1.0 NOV 12, 2024		

$$\% \text{ of the predicted value} = (\text{SVC} / M_{\text{predicted}}) * 100$$

Where

For man:

$$M_{\text{predicted}} = \exp(-11.2281 + 2.4135 * \ln(\text{Height in cm}) + 0.0865 * \ln(\text{Age}) + Mspline)$$

$$Mspline = 0.3298 - 1.1230 * (\text{Age}/100) + 2.8110 * (\text{Age}/100)^2 - 5.4811 * (\text{Age}/100)^3 + 3.5964 * (\text{Age}/100)^4 - 0.5884 * (\text{Age}/100)^5$$

For woman:

$$M = \exp(-10.4030 + 2.2633 * \ln(\text{Height in cm}) + 0.0234 * \ln(\text{Age}) + Mspline)$$

$$Mspline = 0.0745 + 0.6006 * (\text{Age}/100) - 1.0684 * (\text{Age}/100)^2 - 1.1308 * (\text{Age}/100)^3 + 0.9730 * (\text{Age}/100)^4 + 0.0643 * (\text{Age}/100)^5$$

For example, 40 years white man, height 185 cm, SVC of 5L:

$$\% \text{predicted value} = (5/5.79) * 100 = 86 \%$$

For example, 35 years white woman, height 170 cm, SVC of 2.5L:

$$\% \text{predicted value} = (2.5/4.16) * 100 = 60 \%$$

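### A missing month-6 MITOS stage counts as progression even when the same-visit ALSFRS-R items fix the stage, and the SAP neither derives the stage from those items nor checks it against them

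*SAP*

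**What the plan says.** **How the stage is defined.** Protocol 4.2.2.1 says: "The ALS-MITOS score is a more recent staging system composed by 4 key domains included in the ALSFRS-R". The form in Protocol 17.1.2 builds four domains from seven ALSFRS-R items:

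- movement: item 8 or item 6
- swallowing: item 3
- communication: items 1 and 4 together
- breathing: item 10 or item 12

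Its footnotes read "Staging determined by the sum of functional score of 1 for each domain" and "Where two items were used, scoring was based on either or both item scores as indicated". Stage 5 is death and does not come from items.

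**How progression is derived.** SAP 5.2.21 sets the non-progression flag to "0 if ALS-MITOS score is higher at 6 months (or 3 months) compared to ALS-MITOS score at baseline", and to 1 otherwise. It does not say how the score was produced. SAP 5.2 gives the default, open to stated exceptions: "variables derived in the source data will not be re-calculated".

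**Missing data.** Table 2 of SAP 2.3 says: "Missing data at month 6 for whichever reason will be considered as progression". SAP 5.11.3.2.1 repeats the rule but adds a parenthesis that names only death and drop-out before month 6.

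**Timing.** Protocol Table 2 schedules both scales at V3, V4 and the premature discontinuation visit. At baseline they differ: MITOS is rated at V0, while ALSFRS-R is rated at screening and repeated at V0 only if V0 falls more than 15 days later (Protocol 4.1.2, SAP 5.2.2).

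**The concern.** The month-6 stage is the outcome half of a binary endpoint in a small trial, and for a living patient it carries no information beyond seven items rated at the same visit. Two things follow.

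First, the missing-data rule can label as a progressor someone whose stage is known from the V4 items. That error goes one way only: it turns non-progressors into progressors and never the reverse.

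Second, the same seven ratings may sit in the database twice, once as ALSFRS-R items and once behind the MITOS stage. If they disagree, the SAP does not say which governs, and no planned step would reveal it. Communication is the domain to watch in a bulbar-onset population: lost speech alone does not score, because handwriting must be lost too.

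At stake is the month-6 non-progression comparison, which SAP 5.11.1.1 tests at a two-sided 0.20 level.

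**Working it through.** The documents state no figure for MITOS scoring error, missing MITOS forms or power on MITOS, so there is none to reproduce. The check has four steps.

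**1. Is the stage computable from data the analysis already needs?**
The items used are 8, 6, 3, 1, 4, 10 and 12, which makes seven. The month-6 analysis needs item scores anyway, because SAP 5.2.21 sums them into subscores (for example "Bulbar subscore: sum of items 1-3"). So stages 0 to 4 at V3 and V4 can be derived whenever the relevant items are present. The same holds for a premature discontinuation visit that SAP 5.2.5 maps to V3 or V4.

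**2. What is one patient worth?**
The synopsis gives 28 and 14 evaluable patients. Fifty randomised 2:1 gives about 33 and 17 (an inference). The second split is closer to this analysis, because patients with missing data stay in the denominator.

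| Split | IFB-088 | Placebo |
|---|---|---|
| 28:14 | 1/28 = 3.6 points | 1/14 = 7.1 points |
| 33:17 | 1/33 = 3.0 points | 1/17 = 5.9 points |

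**3. Can one patient cross 0.20?**
The counts below are assumed non-progressors, not trial data. Fisher's exact test stands in for the SAP's binomial exact method.

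| IFB-088 | Placebo | Difference (points) | p |
|---|---|---|---|
| 22/28 | 9/14 | +14.3 | 0.459 |
| 22/28 | 8/14 (one placebo form missing) | +21.4 | 0.169 |
| 21/28 (one active form missing) | 9/14 | +10.7 | 0.491 |
| 28/33 | 12/17 | +14.3 | 0.277 |
| 28/33 | 11/17 (one placebo patient to progressor) | +20.1 | 0.151 |
| 28/33 | 13/17 (one placebo patient to non-progressor) | +8.4 | 0.467 |
| 27/33 | 12/17 (one active patient to progressor) | +11.2 | 0.475 |
| 29/33 | 12/17 (one active patient to non-progressor) | +17.3 | 0.242 |

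A single placebo patient moved to progressor crosses 0.20 in both sets. No single change in the active arm crosses it in these examples.

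**4. Which way do the errors run?**
Assume 30% true progression.

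- *Missing month-6 forms.* If 5% are missing at random, 5% of true non-progressors become progressors. The observed rate is 0.30 + 0.05 × 0.70 = 33.5%. This shift is one-directional.
- *Mis-scored forms.* A simulation used symmetric one-stage errors on each form, with 80% of patients at baseline stage 0 and 20% at stage 1.

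| Forms mis-scored | True non-progressors counted as progressors | True progressors counted as non-progressors | Observed progression |
|---|---|---|---|
| 2% | 1.2% | 2.0% | 30.3% |
| 5% | 3.0% | 4.9% | 30.7% |
| 10% | 5.7% | 9.4% | 31.2% |

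Mis-scoring misclassifies patients in both directions and, under these assumptions, barely moves the overall rate.

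**The case against.** The strongest reply is that nothing is shown to go wrong.

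- **Source of the stage.** The sentence in SAP 5.2 does not name MITOS. The eCRF is built for the study, and SAP 5.7 shows that it calculates at least one variable (weight variation). It may compute the stage from entered items. This stands: a reader might infer that sites score the stage by hand, but the documents do not say so. They also do not say that it is computed.
- **The form.** A reader might infer that the form invites raters to score lost speech alone. It prints AND between speech and handwriting and marks the domain with a footnote. Examiners are trained or certified (Protocol 3.1). No error rate is given, so frequent mis-scoring is unsupported.
- **Direction.** A reader might infer that mis-scoring produces false progressors. It does not do so systematically: a V0 stage scored too high, or a V4 stage scored too low, hides progression.
- **Baseline.** V0 falls 2 days to 2 weeks after screening, so ALSFRS-R is normally not rated at V0. The same-visit argument therefore fails for the baseline half of the comparison. This limits the fix.
- **Missing forms.** Protocol 13.2 provides queries for missing and inconsistent data, and the parenthesis in SAP 5.11.3.2.1 may confine the rule to death and drop-out. Both narrow the case. Neither closes it: Table 2 is worded without limit, and no check of MITOS against ALSFRS-R is named.
- **Weight.** The trial is exploratory, not powered for efficacy and without multiplicity adjustment. No decision is tied to p below 0.20. This stands and sets the severity.

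**Conclusion.** The concern holds in limited form. As Table 2 is written, a V4 attendee with complete ALSFRS-R items and no MITOS stage is counted as a progressor although the stage is known. No planned analysis step would detect a disagreement between the recorded stage and the items, whichever way it ran.

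The effect is 3.0 to 7.1 percentage points per affected patient, depending on arm and denominator. Crossing 0.20 was shown only with assumed counts and only for changes in the placebo arm. The number of patients affected is unknown and may be zero. The argument rests on item scores being in the database, which the subscore analysis implies, and on Table 2 being read literally.

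The documents do not support a claim that the endpoint is biased towards progression by mis-scoring, or that hand-scoring is taking place. Severity is minor: a free improvement to a secondary endpoint.

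**What to change.** Amend SAP 5.2.21 and Table 2, and align SAP 5.11.3.2.1 with them:

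1. Derive the V3 and V4 MITOS stage by program from the same-visit ALSFRS-R items, using the domain rules in Protocol 17.1.2. List every disagreement with the recorded stage and resolve it before unblinding.
2. Where the recorded stage is missing, use the derived stage.
3. Count missing as progression only when no stage can be derived. Death remains progression (stage 5).
4. Keep the recorded V0 stage as baseline. Check it against the item scores on the V0 MITOS form if those are in the database. Do not rebuild it from screening ALSFRS-R items.

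The cost is a short derivation program and one discrepancy listing. No new data are needed for the V3 and V4 steps. The V0 check depends on whether the form's item scores were entered, which the documents do not confirm.
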